**1. SYNOPSIS**

Title	A Phase I/II Randomized, Double-Blinded, Placebo-Controlled Clinical Trial to Determine Safety and Feasibility of Using an Acellular Sterile Filtered Amniotic Fluid as a Treatment for COVID-19 Patients.
Short Title	hAF for the Treatment of COVID-19
IRB Number	IRB: 00132922
IND	IND # 23369
Phase	Phase I/II
Design	This is a prospective double-blinded, randomized controlled study to determine the safety and feasibility of using processed sterile filtered amniotic fluid (hAF) to treat and reduce inflammation in COVID-19 patients.
Study Duration	1 year
Study Center(s)	University of Utah
Objectives	
Primary Objectives:
 

• To determine the safety of using processed human amniotic fluid (hAF) intravenously (IV) to treat patients with COVID-19.

• To determine efficacy of hAF vs. placebo to reduce inflammation in COVID-19 patients.

• To determine clinical outcomes in patients treated with hAF vs. placebo.

Number of Subjects	60 patients (30 per treatment arm)
Eligibility Criteria	
Inclusion:
 

1. Age <math>\geq 18</math>

2. SARS-CoV-2 positivity by RT-PCR test, obtained within 14 days of enrollment

3. Hospitalized

4. COVID-19 symptomatic (cough, fevers, shortness of breath, and/or sputum production)

5. Has a room air pulse oximetry of <math>\leq 94\%</math> and requires supplemental oxygen therapy

6. Patients of child bearing potential who agree to use acceptable methods

	
of contraception for 90 days after last administration of study IP
 
7. Patients who are receiving standard of care therapies for COVID-19 that are not FDA approved are eligible for this study
 
8. Patients must be able to consent to the study (e.g. Glasgow Coma Score of <math>\geq 14</math>)
 
9. Patients are required to have controlled blood pressure of <math>< 160/96</math> and have a pulse of <math>< 110</math> at the time of study drug administration.

--	--

	
Exclusion:
 

1. Patients on invasive mechanical ventilation (e.g., endotracheal intubation)

2. Chronic home oxygen utilization

3. Clinically significant home use of immunosuppressive medications, including more than 20mg of steroid (e.g., prednisone) per day, monoclonal antibodies, or chemotherapy medications. Patients who are not chronically immune suppressed are eligible for participation. Patients who are prescribed steroids, including dexamethasone, for the purpose of treating COVID-19 prior to the patient's study hospital admission will not be excluded.

4. Women who are pregnant, breastfeeding or become pregnant during the study

5. Patients on non-invasive positive pressure ventilation

6. Patients on >12 liters per minute via non-rebreather (NRB) or >80% oxygen via high flow nasal cannula

7. Patients who in the opinion of the Investigator has impending respiratory failure, defined as requiring rapidly escalating oxygen supplementation

8. Patients with a hemoglobin < 9 mg/dL

9. Patients diagnosed with Stage 4 or 5 chronic kidney disease (CKD)

10. Patients with diagnosed with Class 3 or 4 congestive heart failure (CHF)

11. Patients with a left ventricular assist device (LVAD)

12. Patients with current thromboembolic phenomena

13. Patients with Type 2 and above heart block

--	---

Randomized, Double-blinded, Placebo-Controlled Clinical Trial to Determine Safety and Feasibility of using an Acellular Sterile Filtered Amniotic Fluid as a Treatment for COVID-19 Patients.

PI: [name]

Version: 17 JUL 2020

	

14. Patients with established positive bacterial blood cultures prior to enrollment

15. Patients with ongoing pericardial effusion, or ascites

16. Patients with clinically significant arrhythmia

17. Patients with liver function tests (ALT or AST) >3x normal

18. Patients with untreated HIV infection

19. Patients diagnosed with end-stage organ disease

Study Product, Dose, Route, Regimen	
hAF will be delivered to the clinical setting on the date of application. Dose is 10mL/day for 5 days; patients may be discharged prior to completing regimen.
 
Route: Intravenous (IV) Push

Statistical Methodology	
One goal of the analysis is to demonstrate safety, which does not require statistical significance.
 
The other primary goal of the analysis is to assess efficacy of hAF by reducing inflammation in COVID-19 patients, potentially leading to improved clinical outcomes. This will be assessed by measurement of C-reactive protein levels before and after the intervention.
 
Secondary outcomes include:
 

1. Death within 30 days

2. ICU-free days at 30 days

3. Hospital length of stay

4. Need for invasive mechanical ventilation

5. Biomarker levels (interleukin-6, d-dimer, lactate dehydrogenase)

6. Need for ECMO

7. Major adverse cardiac events

8. Patient-reported functional status

\*Enrolled subjects will need to meet blood pressure requirements prior to IP administration, detailed below

## 2. STUDY OBJECTIVES

The purpose of this study is to explore the effectiveness of processed human amniotic fluid as a treatment for COVID-19. Past use of human amniotic products (i.e., membrane and fluid) has previously been FDA-approved as a human cells, Tissues, and Cellular and Tissue-Based Products (HCT/P) under 21 CFR 1271 for tissue injury; and has been used to reduce inflammation and fibrosis in patients with a variety of ailments. Given this, we hypothesize that intravenously (IV) administered processed sterile filtered amniotic fluid will reduce inflammation in COVID-19 patients, and improve secondary clinical outcomes. Specifically, we hypothesize that patients who receive IV administered hAF will see a 50% reduction in mean C-reactive protein levels following treatment.

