## 3. ENDPOINTS

### Primary Endpoint:

- C-reactive protein (CRP) levels measured before and after treatment
- Whether the patient experienced any post-randomization, study-related Adverse Events (AEs) while on study (up to 5 days) of treatment.

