- a. Safety assessments will include a defined script inquiring about any new or remaining symptoms (e.g., shortness of breath), sleep quality, if the patient feels they are back to baseline and if they have any positive or negative feedback regarding the IP. Open-ended questions regarding any additional concerns the participant may have as well as a specific question regarding any health events or hospitalizations since the last assessment will also be asked.
- b. These assessments will be performed remotely via telephone by study staff. If the assessment is positive (i.e., if the patient reports AEs that are determined to be related to study drug), a clinician will arrange a telemedicine visit to follow up.

14. At 1, 3, 6, and 12 months post-discharge, patients will be emailed a REDCap survey link in order to complete several surveys: PROMIS measures including Dyspnea Severity, Physical Function, Sleep Disturbance, Anxiety, and Depression, as well as the PTSD Checklist (PCL).

- a. If the patient is still hospitalized at any of these time points, respiratory settings and details of physical therapy progress will be gathered from the chart instead.
- b. Window: 1 month +/- 7 days, 3/6/12 months +/- 14 days

15. If a patient is discharged prior to receiving the 5-days of IP administration the patient will still be followed for the duration of the study

Primary Outcome:

1. C-reactive protein levels as assessed prior to and following intervention.

Secondary Outcomes:

1. Death within 30 days
2. ICU-free days at 30 days
3. Hospital length of stay
4. Need for invasive mechanical ventilation
5. Biomarker levels (interleukin-6, d-dimer, lactate dehydrogenase)
6. Need for ECMO
7. Major adverse cardiac events
8. Patient-reported functional status

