## **8. STATISTICAL CONSIDERATIONS**

### **Statistical Methods**

This is a trial with patients randomized to two groups: (1) treatment group with hAF administered intravenously (n=30), (2) control group with intravenous administration of a saline control (n=30). Both groups will receive standard of care in addition to these treatments.

Descriptive statistics, including mean (SD) and median (interquartile range), will be used to assess patient characteristics, and clinical and biomarker outcomes. Comparisons will be made stratified on ICU vs floor status at enrollment for variables. Categorical characteristics will be compared using chi-square test or Fisher exact test. Continuous characteristics will be compared using independent samples t-test or Wilcoxon-Mann-Whitney test. 95% Confidence intervals and *p*-values will be reported from all comparisons. Statistical analyses will be conducted in R and STATA, significance will be assessed at the 0.05 level and all tests will be two-tailed.

Safety will be assessed by descriptive reporting of the incidence proportion of study-related safety adverse events in each study group, with one-sided 95%

binomial exact confidence intervals. No statistical hypothesis test is planned to assess safety, which is consistent even with large Phase III trials. The table below displays the number of patients, out of 30, experiencing no adverse event and the corresponding lower-bound of the 95% exact confidence interval.

Number of Patients with no Related Adverse Events	Number of Patients Experiencing a Related Adverse Event	Lower-bound of the 95% Exact Binomial Confidence Interval for Safety
30	0	90%
29	1	85%
28	2	80%
27	3	76%

If there are 30 patients in the hAF group and if all patients in the hAF group complete the study without experiencing an adverse event we will be able to state with 95% confidence that the safety of hAF is at least 90%.

Exploratory outcomes for safety include, but are not limited to, the following:

- Whether the patient experienced any post-randomization AEs while on study (regardless of relatedness to study participation)
- Whether the patient experienced any post-randomization serious AEs while on study
- Whether the patient experienced any post-randomization unexpected AEs while on study.

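### The only numeric efficacy hypothesis, a 50% fall in mean CRP in hAF patients, names no comparator and is not tied to the planned between-arm tests

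*Combined protocol and SAP*

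**What the plan says.** The Synopsis lists a comparative objective: "To determine efficacy of hAF vs. placebo to reduce inflammation in COVID-19 patients". Section 2 (Study Objectives) then gives the one efficacy figure: "we hypothesize that patients who receive IV administered hAF will see a 50% reduction in mean C-reactive protein levels following treatment". It names no comparator.

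Three places define the primary efficacy measure, and each gives only the timing of measurement:

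- Synopsis, Statistical Methodology: "This will be assessed by measurement of C-reactive protein levels before and after the intervention".
- Section 3, Primary Endpoint: "C-reactive protein (CRP) levels measured before and after treatment".
- Section 6, Primary Outcome: "C-reactive protein levels as assessed prior to and following intervention".

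Section 6 places the measurements before the first dose and on Day 6.

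Section 8 (Statistical Methods) describes two randomized groups of 30, both on standard of care. Its general rule is that "Continuous characteristics will be compared using independent samples t-test or Wilcoxon-Mann-Whitney test", and "significance will be assessed at the 0.05 level and all tests will be two-tailed". It does not name CRP, Day 6 CRP or change from baseline as the variable for a primary test. The Sample Size Justification gives no effect size, SD, power or expected change on saline.

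**The concern.** The objective and the hypothesis that should make it specific ask different questions. The objective asks whether hAF lowers inflammation more than placebo does. The hypothesis, on its likelier reading, asks whether CRP halves in hAF patients between baseline and Day 6.

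Patients enter while hospitalized and needing oxygen. Both arms receive standard of care, and steroids prescribed for COVID-19 before the study admission are not a reason for exclusion (Section 5). CRP may therefore move between baseline and Day 6 for reasons unrelated to hAF, and the saline arm is there to measure that movement.

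A target without a comparator can mislead in both directions. If CRP falls by half in both arms, the target is met although hAF adds nothing. If CRP rises 20% on saline and falls 40% on hAF, the Day 6/baseline ratio on hAF is half that on saline (0.60/1.20 = 0.50), yet the 50% target is missed. Because the 50% is not an effect against placebo, the result of a between-arm test cannot be judged against it either.

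**Working it through.** **The plan's own figure.** The 30 per arm cannot be reproduced from the CRP hypothesis, because power, SD and saline change are not given. The only figures at n = 30 with complete inputs are the safety lower bounds in Section 8. These do reproduce: the one-sided 95% exact bounds for 30, 29, 28 and 27 of 30 patients free of related events are 90.5%, 85.1%, 80.5% and 76.1%, against 90%, 85%, 80% and 76% stated. They have no bearing on CRP.

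**Inputs for the check.** From the documents: 30 per arm, a 50% target, two-sided 0.05. Assumed: log CRP change is normal with SD *s* between 0.6 and 1.2, and, with no drug effect, both arms share a true geometric-mean fall *f*.

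**Chance that an inert product meets the target.** The observed mean log change in the hAF arm has mean ln(1 − f) and standard error s/√30, so

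P(observed fall ≥ 50%) = Φ( [ln 0.5 − ln(1 − f)] / (s/√30) ).

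Example: f = 0.40 and s = 0.6. The numerator is ln(0.5/0.6) = −0.182, the standard error is 0.6/5.477 = 0.1095, z = −1.66 and P = 4.8%. With s = 1.2 the standard error doubles, z = −0.83 and P = 20%.

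| Shared fall f | s = 0.6 | s = 0.8 | s = 1.0 | s = 1.2 |
|---|---|---|---|---|
| 30% | 0.1% | 1.1% | 3.3% | 6.2% |
| 40% | 4.8% | 10.6% | 15.9% | 20.3% |
| 50% | 50% | 50% | 50% | 50% |
| 60% | 97.9% | 93.7% | 88.9% | 84.6% |
| 70% | >99.9% | >99.9% | 99.7% | 99.0% |

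Simulation with 20,000 trials per setting agrees. The saline arm meets the same target equally often. The hAF-versus-saline test on log change rejects in about 5% of these null trials, or about 2.5% in favour of hAF, whatever the shared fall.

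The protocol says mean CRP without specifying the type of mean. For the arithmetic mean (assumed log SD 0.9 at each visit, baseline–Day 6 correlation 0.5), simulation gives about 5–6%, 20%, 50%, 85% and 99% for shared falls of 30% to 70%, which is the same pattern.

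**What the two readings of 50% imply at 30 per arm.** These use a two-sample comparison of log change.

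- *50% is the hAF–saline difference* (ratio 0.50): power is 99%, 92%, 77% and 61% at s = 0.6, 0.8, 1.0 and 1.2. The number per arm for 80% power is 12, 21, 33 and 48. Thirty per arm reaches 80% only if s is about 0.96 or less.
- *50% is the fall within hAF*: if saline falls 20%, 30% or 40%, the between-arm ratio is 0.50/0.80 = 0.625, 0.50/0.70 = 0.714 or 0.50/0.60 = 0.833. At s = 0.8, power is 62%, 37% or 14%.

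**The case against.** The strongest reply is that this is a randomized, placebo-controlled trial with an objective worded against placebo, and Section 8 plans two-sample tests with confidence intervals and two-tailed p-values. A reader might infer from Section 2 that the saline arm goes unused, or that success will be declared on the hAF fall alone. The documents do not support that. They contain no paired test, no one-sample test against 50% and no decision rule at 50%. This part of the reply stands. It does not close the gap, because the between-arm CRP test has to be inferred: Section 8 speaks of characteristics, never names CRP change, and does not link any test to the hypothesis.

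It can also be said that endpoint text often defines only the patient-level variable and leaves the contrast to the analysis section, and that the Section 2 sentence does not literally say from baseline. That is fair, and the sentence may be incomplete rather than deliberately single-arm. But the analysis section does not supply the missing contrast.

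A further stronger reading is that natural recovery and steroids will halve CRP on saline. The documents give no CRP course under standard care. The steroid text concerns treatment before the study admission, which may already have lowered baseline CRP. The fall on saline is an assumption, and at 30% the chance of meeting the target by default is small.

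Finally, the purpose is exploratory, and the part of Section 4 that appears to report the pilot findings was not available here. A basis for the 50% could lie there. A pilot figure would still not supply the missing comparator in Section 2.

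**Conclusion.** The point holds as a defect in the stated target. The only numeric efficacy hypothesis in the available text has no comparator, the primary endpoint wording gives before and after only, and nothing in Section 8 links the generic two-sample tests to either. As written, the target cannot answer the hAF-versus-placebo question, and an inert product could meet it.

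The size is conditional. With 30 per arm and an assumed SD of log change of 0.6 to 1.2, the chance of meeting the target with no drug effect is roughly 0.1–6% at a shared fall of 30%, 5–20% at 40%, 50% at 50% and 85–98% at 60%. Neither the SD nor the saline fall comes from the documents.

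It does not follow that the trial lacks a between-arm analysis or will claim efficacy from a within-arm fall. Nor does it follow that the 50% was meant as a ratio against saline: putting it there by default would be a new effect-size claim. If saline fell 40%, for example, hAF would have to fall 70% (0.60 × 0.50 = 0.30).

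**What to change.** Before unblinding:

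1. Restate the Section 2 hypothesis and the primary outcome in the Synopsis, Section 3 and Section 6 as a between-arm contrast. One suitable form is the hAF:saline ratio of geometric mean Day 6 CRP, adjusted for baseline by ANCOVA on log CRP.
2. Name that contrast in Section 8 as the primary efficacy test.
3. State that within-arm falls are descriptive only and support no efficacy claim.
4. Have the sponsor say whether 50% means the fall within hAF or the hAF–saline difference. Give the assumed saline change, the log-scale SD and the resulting power at 30 per arm.

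The cost is wording in Sections 1, 2, 3, 6 and 8 plus a short power statement, with no extra patients or samples. The stated target becomes harder to meet, and the power statement may show that 30 per arm is thin for the effect intended.

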## 3. ENDPOINTS

### Primary Endpoint:

- C-reactive protein (CRP) levels measured before and after treatment
- Whether the patient experienced any post-randomization, study-related Adverse Events (AEs) while on study (up to 5 days) of treatment.

### Secondary Endpoint:

- Other endpoints include mean days of supplemental oxygen, mean days of mechanical ventilation, mean ICU and hospital length of stay, and patient-reported functional status.
- Survival at days 7, 14, 60, 90 days post randomization.

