**Exclusion:**

1. Patients on invasive mechanical ventilation (e.g., endotracheal intubation)
2. Chronic home oxygen utilization
3. Clinically significant home use of immunosuppressive medications, including more than 20mg of steroid (e.g., prednisone) per day, monoclonal antibodies, or chemotherapy medications. Patients who are not chronically immune suppressed are eligible for participation. Patients who are prescribed steroids, including dexamethasone, for the purpose of treating COVID-19 prior to the patient's study hospital admission will not be excluded.
4. Women who are pregnant, breastfeeding or become pregnant during the study
5. Patients on non-invasive positive pressure ventilation
6. Patients on  $>12$  liters per minute via non-rebreather (NRB) or  $>80\%$  oxygen via high flow nasal cannula
7. Patients who in the opinion of the Investigator has impending respiratory failure, defined as requiring rapidly escalating oxygen supplementation
8. Patients with a hemoglobin  $< 9$  mg/dL
9. Patients diagnosed with stage 4 or 5 chronic kidney disease (CKD)
10. Patients with diagnosed with NYHA class 3 or 4 congestive heart failure (CHF)
11. Patients with a left ventricular assist device (LVAD)
12. Patients with thromboembolic phenomena
13. Patients with Type 2 and above heart block
14. Patients with established positive bacterial blood cultures prior to enrollment
15. Patients with ongoing pericardial effusion, or ascites
16. Patients with clinically significant arrhythmia
17. Patients with liver function tests (ALT or AST)  $> 3X$  normal
18. Patients with untreated HIV infection
19. Patients diagnosed with end-stage organ disease

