  - a) Patient must have a blood pressure of <160/96 mmHg prior to receiving study IP
  - b) Patient must have a pulse of <110 beats per minute prior to receiving study IP
    - i. In the event that a patient does not meet blood pressure and/or pulse criteria for IP administration, these vital signs will be rechecked every hour until they have returned to the necessary range.
- c. Glasgow Coma Scale
- d. Respiratory support modality and settings
- e. Blood glucose (for patients with diabetes)
- f. Results of chest x-ray and/or chest CT, if available.
- g. Concomitant medications

10. Day 6 (post-intervention) assessment will include:

- a. Vital signs (heart rate, blood pressure, oxygen saturation, respiratory rate, temperature)
- b. Glasgow Coma Scale
- c. Respiratory support modality and settings
- d. Complete blood count with auto differential\*
- e. Complete metabolic panel\*
- f. Blood glucose (for patients with diabetes)
- g. Inflammatory biomarkers (interleukin-6, c-reactive protein, d-dimer, lactate dehydrogenase)\*
- h. Results of chest x-ray and/or chest CT, if available
- i. Concomitant medications

\*Patients who have been discharged from the hospital prior to Day 6 will be asked to return to the hospital or an outpatient clinic for Day 6 lab work.

11. At ICU discharge (if applicable) and hospital discharge, the following will be gathered:

- a. Intervention or control date and time
- b. Vital signs (heart rate, blood pressure, oxygen saturation, respiratory rate, temperature)
- c. Glasgow Coma Scale
- d. Respiratory support modality and settings
- e. Blood glucose (for patients with diabetes)
- f. Results of chest x-ray and/or chest CT, if available.

12. The following data will be collected following hospital discharge:

- a. Last available results of chest x-ray(s) and/or chest CT(s), if available.
- b. ICU admit and discharge dates and times (if applicable)
- c. Hospital floor admit and discharge dates and times
- d. Dates and times of intubation and extubation (if applicable)
- e. Tracheostomy (if applicable)
- f. ECMO status (and settings, if applicable)
- g. Major adverse cardiac events

- h. Discharge date and time
- i. Discharge location
- j. Concomitant medications
  - a) Including but not limited to current COVID-19 therapies not approved by the FDA, and non-pharmaceutical therapies
- k. Date and time of death (if applicable)

13. Safety assessments will be performed at 30, 60, 90 and 180 days (+/- 7 days) post-discharge

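### Hospital, ICU and ventilation durations are to be compared between arms with no rule for patients who die; the likely distortion is modest and cheap to prevent

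*Combined protocol and SAP*

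**What the plan says.** Section 3 (Secondary Endpoint) names plain average durations: "Other endpoints include mean days of supplemental oxygen, mean days of mechanical ventilation, mean ICU and hospital length of stay, and patient-reported functional status".

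The outcome lists in Section 1 (Synopsis) and Section 6 differ from this. Both contain one raw duration, "Hospital length of stay". ICU use appears there as "ICU-free days at 30 days" and ventilation as a yes/no outcome, "Need for invasive mechanical ventilation". Raw ICU and ventilation durations therefore stand only in Section 3. That section does not say whether ventilation means invasive only, although the exclusion list in Section 5 treats "Patients on non-invasive positive pressure ventilation" as a separate category.

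Section 8 (Statistical Methods) states: "Continuous characteristics will be compared using independent samples t-test or Wilcoxon-Mann-Whitney test". It also states: "Comparisons will be made stratified on ICU vs floor status at enrollment for variables". It promises 95% confidence intervals and p-values for all comparisons, two-sided at 0.05.

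Death within 30 days (Sections 1 and 6) and survival at days 7, 14, 60 and 90 (Section 3) are separate outcomes and are not linked to the durations. Section 6 collects the dates of ICU and floor stay, intubation, extubation, discharge and death. No score for a death is given for any duration, nor for ICU-free days.

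**The concern.** Deaths are anticipated, since mortality is an outcome. A patient who dies in hospital or on a ventilator must enter the duration comparison somehow, and two readings are open.

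- **(a) Everyone is included and the stay ends at death.** The direction of a difference in mean stay then depends partly on when deaths occur, because early deaths shorten the mean and late deaths lengthen it.
- **(b) Survivors only.** The groups compared are then defined by an event after randomization, and the arm that loses more of its sickest patients can look better.

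Neither reading isolates recovery when mortality differs between arms, and with no rule fixed the choice could be made after the data are seen. The Synopsis places clinical outcomes among the primary objectives, and Section 10 (Potential Benefits) names shorter hospitalization as a hoped-for gain. A shorter stay caused by early deaths would look like that gain.

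**Working it through.** **Inputs.** From the plan: 30 patients per arm, two-sided 0.05, a Wilcoxon test as one of two options, and a 30-day window for ICU-free days. There is no planned figure for the durations to reproduce. Everything else is assumed, because the available text gives no expected mortality or length of stay (part of the pilot background in Section 4 was not available). Assumptions: survivor stay has mean 12 days (SD 6) and the same distribution in both arms; mortality *m* is 3% vs 6% or 5% vs 10%; deaths occur near day *D* = 6 or 18.

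**Reading (a), fixed stays.** Mean stay = (1 − m) × 12 + m × D.

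- D = 6, 3% vs 6%: 11.64 + 0.18 = 11.82 against 11.28 + 0.36 = 11.64, so the higher-mortality arm looks 0.18 days better.
- D = 6, 5% vs 10%: 11.4 + 0.3 = 11.7 against 10.8 + 0.6 = 11.4, so it looks 0.3 days better.
- D = 18: 12.18 vs 12.36 and 12.3 vs 12.6, so it now looks worse.

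Standard error of the difference: 6 × √(2/30) ≈ 1.55 days (1.53 in simulation).

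**Reading (b), fixed stays.** Suppose 80% of patients stay 10 days and none die, while 20% are severe, stay 20 days if they survive, and carry all the deaths. Survivors' mean = (8 + 20 × (0.2 − m)) / (1 − m).

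- 3% vs 6%: 11.4/0.97 = 11.75 against 10.8/0.94 = 11.49.
- 5% vs 10%: 11/0.95 = 11.58 against 10/0.90 = 11.11.

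**Hospital-free days to Day 30, death = 0.** With the 12-day survivor stay this is (1 − m) × 18, whatever D is: 17.46 vs 16.92 and 17.1 vs 16.2. The measure moves with mortality and does not depend on when deaths occur.

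**Ventilator days.** Assume 20% are ventilated, survivors for 14 days, with all deaths among the ventilated; d = m/0.2. Mean = 0.2 × [(1 − d) × 14 + d × D]. At 5% vs 10%, death after 6 ventilator days gives 2.40 vs 2.00, and death after 20 gives 3.10 vs 3.40. Ventilator-free days = 24 + 3.2 × (1 − d) = 26.4 vs 25.6 in both cases.

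**Simulation.** 20,000 trials per scenario, 30 per arm, unstratified two-sided Wilcoxon. Survivor stay is lognormal (mean 12, SD 6). Time of death is gamma with coefficient of variation 0.4, capped at day 29. For reading (b), stays are lognormal with mean 10 (SD 4) in 80% of patients and mean 20 (SD 6) in the severe 20%. Each cell gives the share of trials in which the result favours the higher-mortality arm, then the share in which it does so significantly.

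| Measure | 3% vs 6% | 5% vs 10% |
|---|---|---|
| Raw stay, deaths near day 6 | 54.7%; 3.22% | 58.0%; 4.00% |
| Raw stay, deaths near day 18 | 45.9%; 1.81% | 42.6%; 1.62% |
| Survivors only | 57.0%; 3.37% | 62.4%; 4.45% |
| Hospital-free days, deaths near day 6 | 37.8%; 1.50% | 31.7%; 1.09% |
| Hospital-free days, deaths near day 18 | 37.1% | 31.2% |

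At equal mortality, raw stay is significant in a given direction in about 2.3% of trials.

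**The case against.** The strongest reply is that this matters little. The bias is a small fraction of the standard error, the endpoints are secondary and unpowered, and mortality is reported alongside, so a reader could notice an imbalance. With late deaths, raw stay already tends to move with mortality. All of this stands and sets the priority. It does not supply the missing rule: separate mortality reporting does not define the duration estimate.

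A second reply is that entry is limited to moderately ill patients, and that Section 7 (Discontinuation of Study) makes any death a trigger for modification or stopping pending a safety investigation. The assumed rates imply 30 × 0.09 = 2.7 and 30 × 0.15 = 4.5 deaths. The chance of at least one is 1 − 0.97³⁰ × 0.94³⁰ = 94% and 1 − 0.95³⁰ × 0.90³⁰ = 99%. An uninterrupted 60-patient trial is thus a simplification. The gap remains, because enrolment may resume and enrolled patients stay in follow-up.

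Third, Section 8 speaks of continuous characteristics. That it covers the durations, with p-values, is the natural reading but not explicit. If it does not, the durations have no stated test at all.

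Fourth, other remedies exist, such as a ranking with death worst, or discharge alive with death as a competing event. Either would close the gap; free days are preferred because the plan already uses one.

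A reader might infer that a misleading result is likely. At 10% vs 20% mortality, the survivors-only model favours the higher-mortality arm in 80% of trials, significantly in 8.0%. That is a ceiling: 20 × (0.2 − 0.2) = 0, so every severe patient in one arm dies. For reading (a) with deaths near day 6, the same rates give a 0.6-day bias and 6.6%. They imply 30 × 0.30 = 9 deaths, which the stopping trigger makes a weak planning case. Nothing in the documents supports treating such rates as expected.

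**Conclusion.** The concern holds as a gap with a modest effect. The plan makes raw durations secondary endpoints and gives no rule for deaths. Reading (a) lets early deaths look favourable, and reading (b) conditions on survival. Under assumed mortality of 3% vs 6% to 5% vs 10% with deaths near day 6, the bias in mean stay is 0.18 to 0.3 days, and significant results in the wrong direction rise from 2.3% to about 3% to 4%. These figures rest on assumed mortality, stay and time of death; the 10% vs 20% cases are upper bounds.

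Two stronger inferences are not supported. The trial's main conclusions are not at risk, since the CRP and safety primaries do not use these durations. Nor does the gap run equally through every outcome list: hospital stay is in all three, but raw ICU and ventilation durations are in Section 3 only, and the other two lists already use ICU-free days, lacking only a score for death. The point deserves correction because the direction of a result should not depend on when patients die and the remedy costs little.

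**What to change.** For the between-arm comparisons, replace the raw hospital, ICU and ventilation durations with days alive and free of hospital, of ICU and of invasive mechanical ventilation from randomization to Day 30, with death by Day 30 scored 0. Give the existing ICU-free days the same score. Define the measures on the index hospitalization and fix the rule before unblinding. Use the same measures in Sections 1, 3 and 6 so that the outcome lists agree.

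Compare by Wilcoxon, one of the two tests Section 8 allows, stratified by ICU or floor status at enrolment. Say so explicitly: the present stratification sentence does not commit to a stratified Wilcoxon and could mean separate comparisons within each stratum. Keep the raw durations, including oxygen days, as descriptive summaries shown separately for survivors and deaths.

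**Cost.** Wording and one derivation. The dates needed for the index stay are already collected under Section 6, and 30-day vital status is already needed for the 30-day death outcome. Downsides: free days are less direct to interpret than days in hospital, the index-stay definition ignores readmissions, and each death enters several correlated secondary outcomes.
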